3. OBJECTIVES, ENDPOINTS, AND ESTIMANDS

Table 4: Study ARGX-113-2010 Objectives and Endpoints

Objectives	Endpoints
Primary	
To assess the long-term safety and tolerability of treatment with efgartigimod PH20 SC in participants with BP	
 • Incidence and severity of treatment-emergent AEs, SAEs, and AESIs • Rate of treatment discontinuation because of safety concerns
Secondary	
To assess the long-term efficacy and durability of response with efgartigimod PH20 SC treatment in participants with BP	
 • Proportions of participants achieving^a: 
 – CR while off OCS for ≥ 8 weeks – CR or PR while off OCS for ≥ 8 weeks – CR while on minimal OCS therapy for ≥ 8 weeks. (Minimal OCS therapy is defined as ≤ 0.10 mg/kg/day of prednisone [or an equivalent dose of another OCS]) – CR while off both OCS and efgartigimod PH20 SC for ≥ 8 weeks^b – CR or PR while off both OCS and efgartigimod PH20 SC for ≥ 8 weeks^b • Duration of sustained remission • Proportion of participants who relapse • Time to relapse • Incidence and severity of relapse • BPDAI activity scores, IGA-BP scores, and itch NRS over time • Rate of treatment failure
Additional secondary	
To evaluate the impact of efgartigimod PH20 SC treatment in reducing long-term glucocorticoid-associated toxicity in participants with BP	GTI-related scores, including the GTI-AIS, GTI-CWS, and GTI-SL over time
To evaluate the impact of efgartigimod PH20 SC treatment on QoL in participants with BP	EQ-5D-5L, DLQI, and ABQoL scores over time
To evaluate the PD and immunogenicity of efgartigimod PH20 SC in participants with BP	
 • Percent change from baseline over time for anti-BP180 and anti-BP230 antibody levels • Incidence and prevalence of ADA against efgartigimod (serum levels)

Objectives	Endpoints
Exploratory	
████████████████████ ████████████████████	██ ████████

^a These endpoint criteria can only be met when participants are off rescue therapy.

^b The endpoint applies only to participants who have stopped receiving efgartigimod PH20 SC before protocol amendment 2 is effective.

No estimands have been defined for this OLE study.

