Similar frequency tabulations will be created for the number and percentage of participants who achieved:

- CR/PROff
- CRmin
- Treatment failure

Similar frequency tabulations, based on the ROL analysis set, will be created for:

- CROff without IMP
- CR/PROff without IMP
- Relapse

Duration of sustained remission and time to relapse will be descriptively presented with median times, quantiles and number and percentage of censored observations and observations with event. Only the participant's first evaluation during the study will be included as observation.

Duration of sustained remission will be presented for the SAF analysis set.

A frequency tabulation will be created for categorized severity of relapse, for the participant's first relapse during the study.

	Statistical Analysis Plan	
ARGX-113-2010	Final analysis	Final 1.0 of 29APR2025

Descriptive statistics will present the actual values, changes and percent changes from study baseline of the BPDAl activity and total scores per analysis visit (baseline and last assessment).

Frequency tabulations will be provided for the outcome of IGA-BP per analysis visit (baseline and last assessment). Additionally, cumulative percentages (starting with the best outcome result) will be calculated.

Descriptive statistics will present the actual values and changes from study baseline of the itch NRS 24-hour average and worst scores per analysis visit (baseline and last assessment).

Descriptive statistics will be provided for the C-GTI scores AIS and CWS at the last assessment.

Frequency tabulations will be provided for the outcomes of the ABQOL (17 items), EQ-5D-5L (5 dimensions) and DLQI (10 items), similar to the frequency tabulations of the IGA-BP outcomes. Descriptive statistics on absolute values and changes from study baseline for EQ-5D-5L VAS score, DLQI score and Total ABQOL score will be calculated per analysis visit (baseline and last assessment), similar to the descriptive statistics of the itch NRS scores.

Listings will be created for:

- Disease status, including the derived response variables (CROff, CR/PROff, CRmin, etc.)
- Duration of sustained remission and time to relapse, including the reason for censoring (if applicable) and the severity of relapse
- Lesion assessments
- BPDAl assessments
- IGA-BP assessments
- Itch NRS assessment
- Calculated C-GTI scores and complementary GTI specific list (GTI-SL)
- ABQOL, EQ-5D-5L and DLQI data

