9. APPENDICES

9.1 GTI: DERIVATION OF CWS AND AIS

9.1.1 Allocate weights

Weights per item are attributed as specified below. GTI at Wx is evaluated versus previous GTI assessment. The first time point is referred to as *start (or previous)* and the second time point within each comparison is referred to as *follow-up (or current)*.

Increase, decrease or no change in medication intake compared to previous assessment are checked in the GTI assessment. A missing evaluation, including for external data, will be considered as no change with weight=0.

External GTI data (i.e., LDL/HbA1c/BP and BMI) are allocated to a GTI assessment based on dates. The last available value of these external data since previous GTI assessment will be used.

Changes from severe to moderate do not have any impact on calculation of CWS/AIS. Severe outcome on an item however is captured on the specific list (SL).

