9.1.1.8 NEUROPSYCHIATRIC EFFECTS (COMPARED TO PREVIOUS ASSESSMENT)

Allocate weights for each of the 4 subitems: insomnia, mania, cognitive impairment, depression

- Moderate/severe to none: -74
- Moderate/severe to minor: -63
- Minor to none: -11
- No significant change: 0
- None to minor: 11
- Minor to moderate/severe: 63
- None to moderate/severe: 74

Notes:

1. presence of psychosis or glucocorticoid-induced violence (as captured in the GTI specific list) always has weight=74. Disappearance of psychosis or glucocorticoid-induced violence has weight=-74.
2. minor and mild or used fully interchangeable

For the derivation from the grading to severe, moderate, minor (or mild): see table underneath:

Minor/Mild	Moderate	Severe (Specific Domain)
Insomnia – (Grade 1)	Insomnia – (Grade 2)	
Mania (Grade 1)	Mania (Grade 2)	Mania (Grade 3)
Cognitive impairment (Grade 1)	Cognitive impairment (Grade 2)	Cognitive impairment (Grade 3)
Depression (Grade 1)	Depression (Grade 2)	Depression (Grade 3)

	Statistical Analysis Plan	
ARGX-113-2010	Final analysis	Final 1.0 of 29APR2025

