9.1.1.9 INFECTION (COMPARED TO PREVIOUS ASSESSMENT)

- No significant infection: 0
- Specific infections < Grade 3 (oral or vaginal candidiasis, uncomplicated zoster): 19
- Grade 3, 4, or 5 or complicated herpes zoster: 93

Note:

Special case domain: each infection is a distinct event, so infections only have worsening. That means that a subject may have Infection grade 3 at Wx and again at Wy and the subjects may be assigned a score of 93 for the worsening from Wx to Wy if the investigator has collected ‘Infection’ at Wy.

	Statistical Analysis Plan	
ARGX-113-2010	Final analysis	Final 1.0 of 29APR2025

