9.1.2 CWS and AIS calculation

9.1.2.1 CWS

The CWS is calculated as the sum of the worsening items: i.e., with weights >0. For the items with subitems, i.e., skin toxicity and neuropsychiatric effects, only the subitem with the highest positive weight is used. As an example, if neither insomnia nor depression were present at the start of the GTI interval but there is mild insomnia and moderate depression present at postbaseline, then only the moderate depression is used for the neuropsychiatric weight (+74 points).

In the CWS calculation, the most severe infection in every GTI interval is scored (so in case of 2 periods, the score for an infection is counted twice for the overall CWS at endpoint).

CWS is calculated at Wx as the sum of the worsening items in all postbaseline timepoints up to that timepoint respectively.

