9.1.2.2 AIS

With the AIS, improvement as well as worsening is included in the calculations of the sum of the items. For the items with subitems, i.e., skin toxicity and neuropsychiatric effects, only the subitem with the highest positive weight is used as well as the subitem with the lowest negative weight is used. For example: if the highest positive skin subitem is +26 and the highest negative skin subitem is -18, then skin weight for AIS is +8.

AIS is calculated at Wx as the sum of the items in all postbaseline timepoints up to that timepoint respectively.

	Statistical Analysis Plan	
ARGX-113-2010	Final analysis	Final 1.0 of 29APR2025

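### GTI-CWS, and to a lesser extent GTI-AIS, is a running sum summarised only at each participant's last assessment, so the pooled figure depends on follow-up length and visit schedule as well as toxicity

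*SAP*

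**What the plan says.** Protocol section 3 names the endpoint as "GTI-related scores, including the GTI-AIS, GTI-CWS, and GTI-SL over time".

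SAP appendix 9.1 builds the scores interval by interval. On the reference point for each weight it says "GTI at Wx is evaluated versus previous GTI assessment". The interval weights are then added up: "CWS is calculated at Wx as the sum of the worsening items in all postbaseline timepoints up to that timepoint respectively", and for the other score, "AIS is calculated at Wx as the sum of the items in all postbaseline timepoints up to that timepoint respectively". CWS adds only positive weights, so it cannot fall. The worst infection is scored once per interval, "so in case of 2 periods, the score for an infection is counted twice for the overall CWS at endpoint". Infection cannot offset itself in AIS either: "Special case domain: each infection is a distinct event, so infections only have worsening".

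For reporting, SAP 4.1.3 says: "Descriptive statistics will be provided for the C-GTI scores AIS and CWS at the last assessment". SAP 2.2.6 defines the last assessment as the last nonmissing postbaseline value, whenever it occurred, and lists AIS and CWS among the parameters that get one. Table 14.2.1.16 is the only C-GTI table. It covers the rollover (ROL) set as one total group (SAP 2.1.2). Other visits appear only in listings.

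**The concern.** Taking the last value is workable for a state measure such as BPDAI or itch. CWS is an accumulating count: its last value depends on how long the participant was followed and into how many intervals that time was cut. The SAP allows for unequal follow-up in the adverse event tables, which give rates per 100 participant-years (SAP 5.1.2), but not here.

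The early stopping may also be informative. Under protocol 7.1.1, treatment failure despite escalated corticosteroid doses, and grade 3 or serious infections considered related, lead to permanent discontinuation of IMP. These participants have a GTI at the early discontinuation visit, but Table 2 schedules none at the two follow-up visits. They stop accruing points at that visit, in an endpoint meant to describe long-term glucocorticoid toxicity. A reader given one pooled mean cannot separate low toxicity from short observation.

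**Working it through.** **1. The SAP's own scoring examples.** Neuropsychiatric CWS with new mild insomnia and new moderate depression: max(11, 74) = 74, as in SAP 9.1.2.1. Skin AIS: 26 − 18 = 8, as in SAP 9.1.2.2. Both reproduce.

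**2. Number of GTI intervals** (protocol 1.3, Tables 1 and 2)
- Table 1: baseline, weeks 24 and 48, giving 2 intervals (24 + 24 weeks).
- Table 2, treated from baseline: baseline, weeks 8, 24, 40 and 48, giving 4 intervals (8 + 16 + 16 + 8 weeks).
- Start on a later day X (weeks 1 to 45): GTI visits are re-timed from day X while the end-of-treatment visit stays at week 48, giving 2 to 4 intervals.
- Early discontinuation visit on Table 2: at week 4, 1 interval; at week 12, 2; at week 30, 3.

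**3. The same course scored on each schedule** (weights from SAP 9.1.1.1, 9.1.1.8 and 9.1.1.9)

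| Course | Table 2 (4 intervals) | Table 1 (2 intervals) |
|---|---|---|
| Grade 3 infection, weeks 4 and 20 | CWS and AIS: 2 × 93 = 186 | 1 × 93 = 93 |
| Grade 3 infection, weeks 4, 16, 30 and 44 | CWS and AIS: 4 × 93 = 372 | 2 × 93 = 186 |
| Neuropsychiatric item moderate only at weeks 8 and 40 | CWS 74 + 74 = 148; AIS 0 | CWS 0; AIS 0 |
| Steady none to minor to moderate (11 + 63 on Table 2) | CWS and AIS 74 | CWS and AIS 74 |
| BMI rising linearly from 26 to 30.5 | CWS and AIS 0 (steps of 0.75 or 1.5 units, below the threshold of 2) | CWS and AIS 21 + 21 = 42 (steps of 2.25) |

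The direction is not fixed: more intervals raise the score for repeated events and fluctuating items, and can hide slow drift.

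**4. Expected infection points.** Assume Poisson grade ≥3 infections at rate λ per 48 weeks. The expectation is 93 × Σ[1 − exp(−λL/48)] over interval lengths L in weeks.
- λ = 0.1: 9.2 (4 intervals), 9.1 (2 intervals), 1.5 (stopped at week 8).
- λ = 1.0: 81.3, 73.2 and 14.3.

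The 4-interval figure exceeds the 2-interval figure by about 1% (9.2/9.1) to 11% (81.3/73.2).

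**5. Illustrative simulation.** All rates are assumptions: 0.3 grade ≥3 infections per 48 weeks, plus one neuropsychiatric item moving weekly between none, minor and moderate under three settings. The same 20,000 courses per setting were scored on each schedule; ranges run over the settings.

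| Schedule | Mean CWS | Mean AIS |
|---|---|---|
| 4 intervals to week 48 | 37.6 to 64.0 | 18.0 to 27.1 |
| 2 intervals to week 48 | 32.9 to 47.2 | 17.2 to 26.2 |
| Stopped at week 24 (2 intervals) | 19.1 to 31.9 | 5.6 to 13.5 |
| Stopped at week 8 (1 interval) | 6.9 to 12.6 | 0.1 to 3.9 |

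**6. Effect on a pooled mean.** Take the middle setting (CWS 48.0 for 4 intervals, 9.2 if stopped at week 8) and assume a share of week-8 stoppers, with toxicity unchanged. At 10%: 0.9 × 48.0 + 0.1 × 9.2 = 44.1. At 30%: 0.7 × 48.0 + 0.3 × 9.2 = 36.4.

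**The case against.** The strongest reply is that little harm follows. This is a descriptive, additional secondary endpoint in a single-arm study with no hypothesis tests, so no between-group comparison is biased. Baseline plus last assessment is the SAP's convention for efficacy tables by visit. Scores at every visit are in listing 16.2.6.7, and phase durations and discontinuations are tabulated. Table 1 covers only participants untreated since baseline who rolled over before amendment 2, and they move to Table 2 once they start IMP, so the 2-interval group may be small.

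That limits the severity but does not remove the point. A listing is not a summary of a named endpoint, and disposition tables do not link follow-up time to the scores. Early stopping distorts the row even if nobody completes Table 1.

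Two further replies are correct. AIS nets improvement against worsening, so graded items largely cancel across intervals: the middle setting gives 21.4 with 4 intervals and 20.6 with 2. And truncation does not always flatter the result. A participant whose item is moderate at week 8 and who leaves then has AIS 74, whereas the week 8 and 40 course above ends at AIS 0 at week 48.

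**Conclusion.** The point holds, mainly for CWS. The last-assessment row mixes sums taken over different follow-up times and numbers of intervals, and it does not deliver the over-time endpoint. Early stopping is the larger distortion: in the illustration, CWS stopped at week 8 is about a fifth of the 4-interval value (6.9/37.6 to 12.6/64.0). The 2-versus-4-interval effect is smaller on average and has no fixed direction. The interval counts follow from the documents; the simulated means rest on assumed rates.

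Three stronger readings are not supported:
- **Table 2 participants score about double.** The 372 against 186 contrast is a ceiling that needs a 93-point infection in every interval. Protocol 7.1.1 also ends IMP for grade 3 or serious infections considered related.
- **The pooled result is biased in the drug's favour.** Stopping early shortens CWS, but the participant keeps the points already scored, AIS can move the other way, and the documents do not show who stops or why.
- **The net bias can be stated.** The share of participants on each schedule and the dropout pattern are not given.

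**What to change.** In SAP 4.1.3 and Table 14.2.1.16:
- Tabulate CWS and AIS at the scheduled GTI weeks, at least weeks 24 and 48, with n at each. Those weeks are common to Table 1 and to Table 2 participants treated from baseline.
- Count these weeks from study baseline (ADY). The windows in SAP Table 3 use AWADY, which restarts with each subperiod and would misplace day-X starters and off-IMP assessments.
- Keep the last-assessment row, and show beside it the follow-up time and the number of GTI intervals contributing. Common weeks align follow-up but not interval counts (1 versus 2 at week 24, 2 versus 4 at week 48), so the count is needed.

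Two alternatives should be avoided. Making week-48 completers the sole headline drops early stoppers and replaces truncation with completer selection. Relying on a split by number of intervals conditions on post-baseline events such as relapse, start date and dropout.

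The cost is a few extra rows, one study-day windowing rule for GTI, and smaller n at later weeks. No new data are needed, because the scores are already derived at each GTI visit.

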9.3. Statistical Analyses

9.3.1. General Considerations

- Descriptive statistical methods will be used to analyze all primary and secondary endpoints. For continuous variables, summaries will include the number of observations (n), mean, SE, 95% CI, median, minimum, and maximum. For categorical variables, summaries will include the number of participants, frequencies, and percentages. No inferential analyses are foreseen.
- AEs will be classified using the latest version of the MedDRA classification system.
- AEs, AESIs, and SAEs will be listed corresponding to MedDRA SOC and PT.
- All AEs will be summarized by relatedness to efgartigimod PH20 SC.
- Any AEs leading to death or discontinuation of efgartigimod PH20 SC will be summarized.
- Multiple occurrences of a single PT in a participant will be counted only once at the maximum severity/grade.
- Laboratory parameters, physical examinations, vital sign measurements, PD, and immunogenicity results will be analyzed descriptively.

The baseline value for ARGX-113-2010 will be the value at the EoTP visit of ARGX-113-2009. All study visits will be recalculated based on actual dates and will be referred to as “analysis

visits” that will be used in the statistical analyses. The rules for calculating the analysis visits and the rules for imputing partial dates or missing dates will be provided in the SAP.

Analyses will not only refer to the baseline of ARGX-113-2010; the baseline value of ARGX-113-2009 may be used for specific analysis as will be outlined in the SAP for this OLE study.

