2.2.6 Last assessment

A last assessment analysis visit will be created as the last available postbaseline assessment with a nonmissing value.

The last assessment will be created for the following parameters:

- BPDAI total and activity score
- IGA-BP
- Itch NRS 24-hour average and worst scores
- ABQOL, DLQI and EQ-5D-5L questionnaires
- GTI AIS and CWS
- Numeric parameters of safety lab, vital signs and ECG

For PD parameters, a last assessment analysis visit will be created per treatment period as the last available post-TPnB assessment with a nonmissing value in the treatment period. Assessments during the follow-up phase will be considered in the selection of the last assessment of the preceding treatment period.

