14.2 EFFICACY DATA

EFFICACY (14.2.1.X)

14.2.1.1	CRoff: Proportion of Participants Who Achieved CRoff	SAF	EFT07b
14.2.1.2	CR/PROff: Proportion of Participants Who Achieved PR/CRoff	SAF	EFT07b
14.2.1.3	CRmin: Proportion of Participants Who Achieved CRmin	SAF	EFT07b
14.2.1.4	CRoff Without IMP: Proportion of Participants Who Achieved CRoff Without IMP	ROL	EFT07b
14.2.1.5	CR/PROff Without IMP: Proportion of Participants Who Achieved CR/PROff Without IMP	ROL	EFT07b
14.2.1.6	Sustained Remission: Kaplan-Meier Estimates of Duration of Sustained Remission	SAF	EFT09a
14.2.1.7	Relapse: Proportion of Participants with Relapse	ROL	EFT07b
14.2.1.8	Relapse: Kaplan-Meier Estimates of Time to Relapse	ROL	EFT09a
14.2.1.9	Relapse: Frequency Tabulation of Severity of Relapse	ROL	EFT07a
14.2.1.10	BPDAI: Descriptive Statistics of Actual Values, Changes From Baseline, and Percent Changes From Baseline in BPDAI Activity Score over Time	ROL	PDT01
14.2.1.11	BPDAI: Descriptive Statistics of Actual Values, Changes From Baseline, and Percent Changes From Baseline in BPDAI Total Score over Time	ROL	PDT01
14.2.1.12	IGA-BP: Frequency Tabulation of IGA-BP Score Over Time	ROL	EFT07d
14.2.1.13	Itch NRS: Descriptive Statistics of Actual Values and Changes From Baseline in Itch NRS 24-hour Average Score over Time	ROL	EFT03a
14.2.1.14	Itch NRS: Descriptive Statistics of Actual Values and Changes From Baseline in Itch NRS 24-hour Worst Score over Time	ROL	EFT03a
14.2.1.15	Treatment Failure: Proportion of Participants with Treatment Failure	ROL	EFT07b
14.2.1.16	C-GTI: Descriptive Statistics of CWS and AIS over Time	ROL	EFT03a
14.2.1.17	ABQOL: Frequency Tabulation of ABQOL 17 Items Over Time	ROL	EFT07d

	Statistical Analysis Plan	
ARGX-113-2010	Final analysis	Final 1.0 of 29APR2025

14.2.1.18	ABQOL: Descriptive Statistics of Actual Values and Changes From Baseline in ABQOL Total Score over Time	ROL	EFT03a
14.2.1.19	EQ-5D-5L: Frequency Tabulation of EQ-5D-5L 5 Dimensions Over Time	ROL	EFT07d
14.2.1.20	EQ-5D-5L: Descriptive Statistics of Actual Values and Changes From Baseline in EQ-5D-5L VAS Score over Time	ROL	EFT03a
14.2.1.21	DLQI: Frequency Tabulation of DLQI 10 Items Over Time	ROL	EFT07d
14.2.1.22	DLQI: Descriptive Statistics of Actual Values and Changes From Baseline in DLQI Score over Time	ROL	EFT03a
PHARMACODYNAMICS (14.2.3.X)			

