16.2.6 INDIVIDUAL EFFICACY RESPONSE DATA		
16.2.6.1	Disease Status	ROL
16.2.6.2	Duration of Sustained Remission, Time to Relapse and Severity of Relapse	ROL
16.2.6.3	Lesion Assessments	ROL

Statistical Analysis Plan

ARGX-113-2010

Final analysis

Final 1.0 of 29APR2025

16.2.6.4	BPDAI	ROL
16.2.6.5	IGA-BP	ROL
16.2.6.6	Itch NRS	ROL
16.2.6.7	C-GTI	ROL
16.2.6.8	GTI Specific List	ROL
16.2.6.9	ABQOL	ROL
16.2.6.10	EQ-5D-5L	ROL
16.2.6.11	DLQI	ROL
16.2.6.12	[REDACTED]	ROL
16.2.6.13	Anti-BP180 and Anti-BP230 Antibodies	ROL
16.2.6.14	Efgartigimod Anti-drug Antibodies and Neutralizing Antibodies	ROL

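### GTI-SL is a named additional secondary endpoint, and the place the SAP assigns to severe item outcomes, but the SAP only lists it and does not summarise it

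*SAP*

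**What the plan says.** The endpoint for the glucocorticoid-toxicity objective, in the additional secondary group, is "GTI-related scores, including the GTI-AIS, GTI-CWS, and GTI-SL over time" (Protocol section 3, Table 4; SAP Table 1 has the same wording). Protocol 9.3.1 sets the general rule: "Descriptive statistical methods will be used to analyze all primary and secondary endpoints". For categorical variables it specifies frequencies and percentages.

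SAP 4.1.3 then plans two different treatments:

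- For the composite scores: "Descriptive statistics will be provided for the C-GTI scores AIS and CWS at the last assessment".
- For the specific list, only an entry among the listings: "Calculated C-GTI scores and complementary GTI specific list (GTI-SL").

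The output lists match this. The only GTI table is 14.2.1.16, "C-GTI: Descriptive Statistics of CWS and AIS over Time". The specific list is Listing 16.2.6.8, "GTI Specific List". The last-assessment visit in SAP 2.2.6 is created for "GTI AIS and CWS" and not for GTI-SL.

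SAP 9.1.1 says that moving from severe to moderate leaves CWS and AIS unchanged, and adds: "Severe outcome on an item however is captured on the specific list (SL").

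**The concern.** A named endpoint component gets no descriptive summary although the protocol commits to one. SAP 6.1, the place for changes that no amendment covers, shows no entry, so the departure is not declared. Every other unredacted secondary endpoint in SAP Table 1 has at least one table in SAP 8.1. The quality-of-life instruments are even tabulated item by item (17 ABQOL items, 5 EQ-5D-5L dimensions, 10 DLQI items). GTI-SL is the exception, which looks like an oversight.

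Two kinds of information are at stake: the GTI-SL domains that never enter the composite, and the distinction between severe and moderate for items where the composite weights merge the two grades. As planned, a reader of the study report could recover either only by working through individual listings.

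**Working it through.** The plan states no figure to reproduce. The check traces the three components through the documents and then reads the weights.

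**Step 1. Trace each component.**

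| Component | Named endpoint | Last-assessment visit (SAP 2.2.6) | Summary table (SAP 8.1) | Listing (SAP 8.2) |
|---|---|---|---|---|
| GTI-AIS | yes | yes | 14.2.1.16 | 16.2.6.7 |
| GTI-CWS | yes | yes | 14.2.1.16 | 16.2.6.7 |
| GTI-SL | yes | no | none | 16.2.6.8 |

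Result: 2 of 3 components are summarised and 1 of 3 is not.

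**Step 2. What GTI-SL holds (Protocol 8.3.6).** It has 11 domains, 9 of them shared with the C-GTI: 11 − 9 = 2 domains outside the composite. It has 23 items, one of which (bone mineral density decrease) is not used: 23 − 1 = 22 used items. Items tabulated: 0 of 22.

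**Step 3. How the composite treats severe grades (SAP 9.1.1.6 and 9.1.1.8).** Both sections use a single class for moderate and severe.

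- Skin: none to minor +8, minor to the pooled class +18, none to the pooled class +26. Check: 8 + 18 = 26.
- Neuropsychiatric: +11, +63 and +74 for the same steps. Check: 11 + 63 = 74.

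Moving from moderate to severe does not change class and no weight is given for it, so it scores 0. A participant who goes from none to moderate and then to severe accumulates 26 + 0 = 26 (skin) or 74 + 0 = 74 (neuropsychiatric), the same as one who stays at moderate.

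**Step 4. How many subitems this affects.** The grading tables give a severe grade to 3 of 5 skin subitems (acneiform rash, atrophy/striae, erosions/tears/ulcerations) and to 3 of 4 neuropsychiatric subitems (mania, cognitive impairment, depression). That is 3 + 3 = 6 of 9. Easy bruising, hirsutism and insomnia have no severe grade.

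**Step 5. Severe outcomes that do score.** Hypertensive emergency or PRES scores +44 (SAP 9.1.1.3). Psychosis or steroid-induced violence, itself read from the GTI-SL, scores +74 (9.1.1.8). Infection of grade 3 to 5 or complicated zoster scores +93 (9.1.1.9).

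**Step 6. Adverse-event tables.** Table 14.3.1.8 covers serious prednisone-related events, 14.3.1.11 prednisone-related events of any grade, and 14.3.1.9 events of grade 3 or more from any cause. All three are limited to treatment-emergent events in the SAF set. No table gives prednisone-related events of grade 3 or more, and none reports GTI-SL items.

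**The case against.** The case for leaving the SAP alone has four parts.

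- Severe steroid toxicity is not hidden. It adds points to CWS and AIS, several severe events have their own weights (step 5), and three adverse-event tables bear on it (step 6). This stands, and it limits the point. It does not replace the missing summary. Protocol 8.3.6 presents the GTI as a complement to adverse-event reporting. Two of the tables depend on the investigator attributing the event to prednisone, the third ignores cause, and seriousness is a different scale from severity (Protocol 10.3.3).
- GTI-SL is the lesser instrument. Protocol 8.3.6 treats the C-GTI as primary and GTI-SL as unweighted supporting information, and the study is single-arm with no hypothesis tests. This also stands, so the count of one component in three should not be read as a third of the endpoint's importance. The endpoint still names GTI-SL.
- The zero score for moderate to severe is inferred. SAP 9.1.1 states only the opposite direction. That is correct: the zero follows from the pooled weights, and only for the six subitems. The myopathy weights (9.1.1.5) are not in the text available, so nothing is claimed for that domain.
- A table with a column for every GTI assessment would clash with SAP 4.1.3, which shows only baseline and last assessment. Columns would also not align, because Protocol SoA Table 1 places GTI at weeks 24 and 48, while Table 2 uses week 8 and then every 16 weeks, plus week 48. This stands, and the fix below follows the SAP's convention.

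**Conclusion.** The SAP leaves a named endpoint component without the descriptive analysis that Protocol 9.3.1 promises, and does not record the departure. In size: 1 of 3 named components unsummarised, 0 of 22 used items tabulated, 2 domains outside the composite, and 6 of 9 skin and neuropsychiatric subitems in which severe cannot be told from moderate in the tabulated scores. The documents give no event rates, so the number of participants affected cannot be estimated.

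A reader might infer that GTI-SL is the only place where severe steroid toxicity is captured, that the tabulated scores cannot show it, or that it appears in no summary table. The documents do not support any of these readings. Severe outcomes enter CWS and AIS, either pooled with moderate or through their own weights, and Tables 14.3.1.8, 14.3.1.9 and 14.3.1.11 cover part of the same ground. Nor is the objective to prove a reduction in toxicity; it is to evaluate the impact of treatment.

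This is a gap in completeness that should be closed before the analysis. It does not threaten the primary safety objective. The conclusion assumes that the output lists in SAP 8.1 and 8.2 are complete as shown.

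**What to change.** In SAP 4.1.3 and 8.1, add one frequency table in the ROL set. For each used GTI-SL item, give n (%) of participants with the item present at study baseline, present at last assessment, and newly present at any postbaseline assessment. The denominator is participants with nonmissing GTI-SL; for the newly-present column, that means nonmissing at baseline and at least once afterwards. Add GTI-SL to the last-assessment list in 2.2.6 and keep Listing 16.2.6.8.

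The cost is SAP wording and one extra descriptive table from data already collected and listed, with no protocol amendment. The baseline column relies on SAP 2.2.2, under which values from the end-of-treatment visit of ARGX-113-2009 are copied into this study's database. If the sponsor prefers to list GTI-SL only, the minimum is to state that in SAP 6.1 with the reason.
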